10. Cycle cancellation is defined generally as a cycle in which ovarian stimulation or monitoring has been initiated with the intention to treat, but which did not proceed to follicular aspiration or, in the case of a thawed or warmed embryo, did not proceed to embryo transfer. Information on cycle cancellation will be ascertained in the IVF registers.
11. Ovarian hyperstimulation syndrome is defined generally as an exaggerated systemic response to COS characterized by a wide spectrum of clinical and laboratory manifestations. It will be ascertained in this study based on a recorded primary or secondary diagnosis of OHSS within inpatient or outpatient specialized care within 70 days (10 weeks) after oocyte retrieval or as recorded in the IVF registers in a given IVF/ICSI stimulation cycle. For descriptive purposes, OHSS will be classified as early if it occurred within 9 days after oocyte retrieval, and late if it occurred 10 or more days after oocyte retrieval. The day of hospital admission (inpatient care) or hospital visit (outpatient care) will be defined as the onset of OHSS (23). A woman may experience both early and late OHSS. Thus, for the description of OHSS, a woman may be counted towards the early and late classification in a given cycle. For the combined measure to be used in the comparative analyses, only one occurrence of OHSS per cycle will be counted. If a new cycle was initiated within 70 days after oocyte retrieval, the previous stimulation cycle will be excluded from further descriptive and comparative analyses with respect to OHSS from the date of treatment start for the new cycle. The diagnosis code used to ascertain OHSS is provided in Appendix 3 (Section 14.3.1).
12. Treatment-associated costs are defined as direct medical costs of treatments (drugs and other treatments), pregnancy loss/birth, and adverse events (*i.e.*, OHSS) resulting from an IVF/ICSI stimulation cycle.

Detailed definitions for ascertainment of the secondary outcomes using ICD-10 and procedure codes, as applicable, are provided in Appendix 3 (Section 14.3.1). For the calculation of the secondary outcome measures, refer to Section 9.7.3.3 (Table 7).

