9.3.2 Other Variables (Covariates)

In addition to the outcome and exposure variables outlined in Section 9.1.2 and Section 9.3.1, the covariates of interest in this study are listed below and classified according to their intended use in the analysis (Table 1).

The variables are generally described as measured in relation to each IVF/ICSI stimulation cycle; however, variables used to derive the outcome variables may also apply to any linked FET cycles, depending on the outcome under study. Variables indicated as being candidates for regression modeling are determined after the decision on which gonadotropin to use for COS has been made. These variables will therefore not be included in the PS but may instead be added as independent covariates in the IPTW-weighted regression model (see Section 9.7.3.1 for further details).

For variables identified in the registers by ATC, ICD-10 and/or procedure codes, these operational definitions are provided in Appendix 3 (Section 14.3.3).

Table 1. List of covariates and their use in the study

Variable	Measurement scale	Baseline characteristic	Candidate variable for PS	Candidate variable for additional adjustment
Demographic characteristics				
Age at stimulation cycle index date	Continuous	X	X	
IVF/ICSI treatment characteristics				
Treatment type (ICSI, IVF, ICSI + IVF; FET)	Categorical	X	X	
Type of clinic (private, public)	Categorical	X	X	
Calendar year of stimulation cycle	Continuous	X		
GnRH protocol (agonist, antagonist)	Categorical	X	X	
Cycle cancellation (timing within cycle)	Categorical	N/A (used to derive outcome variable)		
Date of cycle cancellation	Continuous	N/A (used to derive outcome variable)		
Type of drug for ovulation triggering	Categorical	X		X

Variable	Measurement scale	Baseline characteristic	Candidate variable for PS	Candidate variable for additional adjustment
Type of drug for luteal phase support	Categorical	X		X
Date of follicular aspiration	Continuous	N/A (used to derive outcome variable)		
Date of embryo transfer	Continuous	N/A (used to derive outcome variable)		
Number of days of embryo cultivation ⁺	Numerical	X		X
Date of embryo cryopreservation	Continuous	N/A (used to derive outcome variable)		
Embryo cryopreservation method (slow freezing, vitrification)	Categorical	X		X
Date of embryo thawing	Continuous	N/A (used to derive outcome variable)		
Number of embryos thawed	Continuous	N/A (used to derive outcome variable)		

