9.7.2 Derived and Transformed Data

The data sources included for this study are national healthcare registers that are expected to have a comprehensive coverage and high-quality data. Thus, large amounts of missing data is not expected to be an issue in this study. In case of missing data, a missing data category will be added, and the number of observations and patients with missing data will be reported for each measured variable in the study. The handling of missing data will be described in more detail in the SAP.

The IVF registries may record some of study covariates related to patient characteristics (see Table 1, section 9.3.2), such as smoking status or BMI, only for the patient's first stimulation cycle. Thus, the covariate value from the patient's first stimulation cycle will be used also for the patient's subsequent cycles if the covariate values for the subsequent cycles are missing.

Any study variables and outcomes that are only recorded if an event occurs, such as live birth, are not considered missing. Also, any outcomes relying on the presence of a diagnostic code (i.e. ICD-10), such as OHSS, fit this definition.

Any derived and transformed data needed for conducting the statistical analysis will be described in the SAP.

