9.7.3.1 Propensity Score Methodology

PS-based methods are frequently used in non-interventional studies to control for confounding when estimating treatment effects (38). In this study, the PS weighting will be implemented using IPTW approach.

PS, typically obtained using logistic regression models, are covariate summary scores that indicate the individual probability of having a treatment initiated with the study drug against the comparator drug, given the observed baseline characteristics. In PS weighting with IPTWs, each subject is weighted by the inverse probability of receiving the treatment they have actually received, *i.e.*, $1/PS$ in the study drug cohort and $1/(1-PS)$ in the comparator drug cohort (22). In other words, the PS weighting with IPTW creates a pseudo-population of study drug cohort and the comparator drug cohort that are weighted samples of the original study cohorts but have the same covariate distribution as the overall original study cohorts (22). Thus, using the IPTW-weighted study cohorts will remove confounding from all covariates included in the PS model, and give the estimate for the treatment effect in the overall population (22).

For this study, the IPTW approach will be based on pairwise PS estimation for i) rhFSH-alfa reference product cohort and HP-hMG cohort, and ii) rhFSH-alfa reference product cohort and rhFSH-alfa biosimilars cohort. The PS will be estimated for the stimulation cycle initiation with the study drug (rhFSH-alfa reference product) against the comparator drug (HP-hMG or rhFSH-alfa biosimilar product) by using logistic regression, including covariates as indicated in Table 1 (Section 9.3.2). Based on the estimated pairwise PS, i) IPTW-weighted rhFSH-alfa reference product cohort and IPTW-weighted HP-hMG cohort, as well as ii) IPTW-weighted rhFSH-alfa reference product cohort and IPTW-weighted rhFSH-alfa biosimilars cohort will be created.

Diagnostic measures will be used for assessing the success of the PS model to account for confounding. In addition, the distribution of IPTWs will be checked and in case very large weights are observed, the stabilized, trimmed and truncated weights will be considered to avoid increasing the variability of the treatment effect estimates due to very large weights (38).

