PS weighting and evaluation of its success will be done separately per each analysis set (see Section 9.7.1) as covariate balance is not automatically the same in the analysis sets that include data from slightly varying time periods and thus have may have slightly varying set of data included. Also, for stratified analyses, PS weighting and evaluation of its success will be re-done as covariate balance is not automatically maintained in the sub-groups that are created by the stratification.

In addition, other PS implementation methods, such as matching or stratification, may be considered in case the received data does not support for using IPTW approach, for any reason.

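### Treatment type, including ICSI + IVF and FET, is a propensity score candidate with no limit to the method planned at stimulation start, which can attenuate the cancellation odds ratio

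*Protocol*

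**What the plan says.** Section 9.3.2 explains why some covariates are reserved for additional adjustment: they "are determined after the decision on which gonadotropin to use for COS has been made". The consequence is stated next: "These variables will therefore not be included in the PS but may instead be added as independent covariates in the IPTW-weighted regression model". Table 1 treats the ovulation trigger, luteal phase support, days of embryo cultivation and cryopreservation method in this way.

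The Table 1 row "Treatment type (ICSI, IVF, ICSI + IVF; FET") is marked instead as a baseline characteristic and PS candidate. Section 9.7.3.1 estimates the PS "by using logistic regression, including covariates as indicated in Table 1 (Section 9.3.2") and adds that "PS weighting and evaluation of its success will be done separately per each analysis set".

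Four other provisions matter:

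- **Cohort entry (9.2.2).** A cycle needs only to be initiated, so cancelled cycles stay in the cohorts.
- **Cancellation (9.1.2.2).** A cancelled stimulation cycle is one that was started but "did not proceed to follicular aspiration".
- **Missing data (9.7.2).** "In case of missing data, a missing data category will be added". The same section says that variables recorded only when an event occurs do not count as missing.
- **Analysis (9.7.3.4).** Cancellation is a binary outcome per initiated stimulation cycle, compared by an IPTW-weighted OR.

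**The concern.** A PS should hold only what is known when the drug is chosen. Two parts of this variable do not meet that test. FET describes a later cycle, and the method as performed, above all a split of the retrieved oocytes between ICSI and IVF, requires oocytes to exist. Nothing in Table 1 limits the variable to the method planned at stimulation start.

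A cycle cancelled before aspiration has no performed method. If the register field is then blank, the blank becomes a level of a PS covariate, and that level is partly a marker of the outcome. IPTW makes the level equally frequent under both drugs and so balances part of the cancellation difference away. Cancellation is one of the protocol's safety objectives. Effectiveness outcomes analysed per initiated cycle, such as CLBR, would also lose the part of the drug effect that acts through cancellation.

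**Working it through.** The plan gives no figure for this point, and the study size in Section 9.5 rests on MC-CLBR, so there is nothing to reproduce. The check asks how far the weighted cancellation OR moves.

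**Inputs**

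- Cycles: n1 = 53,000 (reference product) and n0 = 33,000 (HP-hMG), Denmark from 2010, Table 2.
- Cancellation: c1 = 8%, c0 = 10%. Assumed; the protocol gives no rates.
- f = share of cancelled cycles with blank treatment type. Not in the protocol; varied from 0 to 100%. No other cycle is blank.
- The ICSI/IVF split is the same in both arms, so among cycles with a recorded type the PS does not depend on type.

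**Formula.** With weights 1/PS and 1/(1 − PS), each level of treatment type has its pooled frequency in both weighted arms. The blank level has weight

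m = f × (n1·c1 + n0·c0) / (n1 + n0)

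Every blank cycle is cancelled, so the weighted risk in arm a is

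r_a = m + (1 − m) × c_a(1 − f) / (1 − f·c_a)

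The OR is the ratio of the odds of r1 and r0.

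**Case f = 50%**

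- Pooled cancellation: (4,240 + 3,300) / 86,000 = 0.0877, so m = 0.0438.
- Reference: 0.0438 + 0.9562 × 0.04/0.96 = 0.0837.
- HP-hMG: 0.0438 + 0.9562 × 0.05/0.95 = 0.0942.
- OR = (0.0837/0.9163) / (0.0942/0.9058) = 0.878, against a true (0.08/0.92) / (0.10/0.90) = 0.783.

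**All cases**

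| Share of cancelled cycles blank | r1 | r0 | Weighted OR |
|---|---|---|---|
| 0% | 0.080 | 0.100 | 0.783 |
| 25% | 0.082 | 0.097 | 0.828 |
| 50% | 0.084 | 0.094 | 0.878 |
| 75% | 0.086 | 0.091 | 0.935 |
| 100% | 0.088 | 0.088 | 1.000 |

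**Variations**

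- *Blanks elsewhere.* If all cancelled cycles are blank and so are 2% or 5% of the other cycles, the OR is 0.956 or 0.913.
- *Other rates.* For 5% vs 8% (true 0.605) the five values are 0.605, 0.681, 0.769, 0.874 and 1.000. For 10% vs 15% (true 0.630) they are 0.630, 0.698, 0.779, 0.878 and 1.000.
- *Other cohorts.* The formula depends on the ratio n1:n0, not on total size, so an equal eligibility loss in both arms changes nothing. For 8% vs 10% at f = 50%, the Swedish HP-hMG comparison (42,000 vs 40,000) gives 0.880 and the Danish biosimilar comparison (31,000 vs 5,000) gives 0.875.
- *Logistic PS.* A simulation with one confounder and a main-effects logistic PS (true marginal OR 0.602) gives 0.619, 0.694, 0.778, 0.865 and 1.001 for the same five shares. Without treatment type in the PS it gives 0.619.

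**Live birth per initiated cycle.** Assume 30% live birth in every non-cancelled cycle, so that the drugs differ only through cancellation. The rates are 0.92 × 0.30 = 0.276 and 0.90 × 0.30 = 0.270, a true OR of 1.03. With all cancelled cycles blank, both weighted rates become (1 − 0.0877) × 0.30 = 0.274 and the OR is 1.00.

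**The case against.** **The register content is unknown.** Section 9.4.1 says only that the Danish register holds the fertilisation method. A method planned before stimulation is a legitimate baseline variable, and if it is recorded for every initiated cycle the mechanism above does not arise. This stands, and it is why the size is given as a range that starts at no bias.

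**The exclusion sentence is narrower than a general rule.** Literally, it covers the variables in the additional-adjustment column, and treatment type is not among them. That is correct. But the reason it gives, timing after the drug decision, applies equally to FET and to a performed method, so the conflict is with the protocol's own rationale. Table 1 also says candidate, so entry into the PS is planned rather than certain.

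**Section 9.7.2 may not class such blanks as missing.** A field empty because no retrieval took place could fall under its rule for event-dependent variables. This does not cure the problem, because any separate level for those cycles acts in the PS as a missing level does.

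**FET may be an empty level.** The PS is for stimulation cycle initiation, and FET cycles inherit the cohort of the cycle they came from. That largely stands, although Table 7 counts linked FET cycles in the cancellation denominator.

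**Removing the variable could do harm.** Table 1 gives male factor infertility for Denmark only, and the female infertility code list in Section 14.3.3 excludes infertility associated with male factors. This stands and shapes the fix.

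**Stronger readings.** A reader might infer that the fertilisation method exists only after retrieval, or that the weighting removes the drug effect on cancellation. The protocol supports neither. It never says that the performed method is meant, and complete removal requires blank to coincide exactly with cancelled.

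**Conclusion.** The point holds as a conditional one. Table 1 admits to the PS a variable with one level (FET) that cannot be known at the start of a stimulation cycle, and it does not restrict the others to the planned method. Followed as written, the plan can weight on post-stimulation information.

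The consequence for secondary objective 7 runs from none to complete. At the assumed 8% vs 10%, a true OR of 0.78 is estimated anywhere between 0.78 and 1.00, according to the share of cancelled cycles that are blank. The cancellation rates and that share are assumptions. The direction, towards 1, is not sensitive to the rates tried. This is a statement about bias in the OR, not about power.

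CLBR, analysed per initiated cycle, would be affected through the same route. For LBR it depends on which text is followed: Table 6 makes the initiated cycle the unit of analysis, whereas Section 9.7.3.4 models live birth per fresh embryo transfer, where cycles cancelled before aspiration do not enter. A reader might infer that all live birth results are affected; the protocol does not settle that.

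**What to change.** In Table 1, drop the FET level and define treatment type for the PS as the method planned at stimulation start, usable only if it is recorded for all initiated cycles, cancelled ones included. Check this in each register before the PS is specified, by tabulating blank treatment type against cancellation without splitting by drug.

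Where only the performed method is available, leave it out of the PS and also out of the outcome model for outcomes per initiated cycle. Moving it to the additional-adjustment column would condition on the same post-stimulation information. Show the PS that includes it as a sensitivity analysis.

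The cost is a reworded table row and one tabulation per country. The real downside is in Sweden: if only the performed method is held there, a proxy for male factor is lost, with no listed variable to replace it. The sensitivity analysis shows how much the results depend on that, and the loss should be stated as a limitation.

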The overall study period will be between 2010 and 2020. Different study period starts will be applied depending on which two drugs are being compared. For the comparison between rhFSH-alfa reference product and HP-hMG, the study period will start 1 January 2010 for both countries. This date is selected to ensure the study is sufficiently powered while also reducing heterogeneity in patient management over time. Changes that have occurred over time include moving towards vitrification rather than slow freezing for embryo cryopreservation and hence also moving from cleavage stage to blastocyst embryo transfers, elective single embryo transfers rather than double embryo transfers, and antagonist protocols rather than agonist protocols. For the comparison between rhFSH-alfa reference product and rhFSH-alfa biosimilar products, the study period will start 26 March 2014 for Denmark and 20 June 2014 for Sweden. These are the earliest dates when a rhFSH-alfa biosimilar product (Bemfola) received reimbursement status in each country. For

Sweden, where the IVF register is updated annually and has a lag time of approximately two years (see Section 9.4.2), inclusion of women undergoing IVF/ICSI treatment may end on 31 December 2019, depending on data availability at the time of data extraction. No such general restriction will be applied for Denmark, as the IVF register is updated monthly. In terms of follow-up of IVF/ICSI treatment and pregnancy outcomes, the study will end on 31 December 2020 (or last available date) for each country. Specifically, for the main analyses of the primary objective (LBR, CLBR and MC-CLBR) and secondary objective 4 (TTLB), a minimum follow-up period of 1 year has been chosen to allow sufficient time to achieve (at least) one live birth and a reasonable number of complete cycles for reliable estimates of live birth rates. Hence, the corresponding analyses are restricted to cycles initiated on or before 31 December 2019 (Sets 1 and 5 in Table 5). The minimum follow-up period will be extended to 2 years in a sensitivity analysis to explore the potential effect this has on the estimated MC-CLBR and TTLB (see sensitivity analysis 3 in Table 8).

To reduce possible bias linked to confounding by baseline characteristics, inverse probability of treatment weighting (IPTW), based on propensity scores (PS) (22), will be used to balance the distribution of potential confounders across the study cohorts.

Figure 1. Study design

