9.4 Data Source

The Danish and Swedish data sources are the property of, maintained and made accessible for research by permission of governmental and regional authorities. The health care system is a tax-funded, one-payer system with coverage for all residents and only little co-payment from the patients.

Since introducing the Danish Civil Registration System in 1968, demographics (age, sex, geographical region), migration and vital statistics data have been registered electronically on a daily basis for all Danish residents. Civil registration in Sweden dates back to the 17th century and was transferred from the local parishes to the state in 1991. Demographic data (age, sex, geographical region), migration and vital statistics data for all Swedish residents can be found in the Total Population Register (held by Statistics Sweden) from 1968 onwards.

Every individual in Denmark and Sweden is provided with a unique personal identification number at birth or upon immigration which allows for follow-up until death or emigration. The personal identification number is used for many administrative purposes, such as an identifier in population and health care registers.

The personal identification number forms the basis for the precise, deterministic linkage of individual-level data between different registers and databases in Denmark and Sweden. Given that the personal identification number is used as a unique identifier for a multitude of purposes, it allows for the creation of a tailored database with individual-level data for any given study.

The Danish and Swedish health care data sources are typically established as registers for other reasons than research (examples: control and funding of hospitals, payment of general practitioners for services provided to patients, control system for patients' co-payment of prescription drugs, and authorities' control of treatments using assisted reproduction techniques). Thus, the registers are a mirror of clinical practice in each country. Furthermore, the data sources are also used extensively for epidemiological research.

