9.4.2 Sweden

The Swedish National Quality Registry of Assisted Reproduction (Q-IVF) is maintained by a regional health authority, the Region Västra Götaland, and has data since 2007. The Q-IVF covers virtually 100% of IVF treatments in the Swedish population (10.4 million in 2020). It contains information on all IVF and IUI records from all IVF clinics in Sweden (currently, 6 public and 13 private). The information in the register includes a range of patient characteristics, all IVF and insemination treatments and their results (including pregnancy outcome). Approximately 20,000 IVF treatments per year are included in the register. Between 1982 and 2006, data was directly reported to the National Board of Health and Welfare with only clustered data (*i.e.*, without personal identification numbers). The Q-IVF used to be updated on a yearly basis, with data on IVF treatments and treatment outcomes becoming available approximately 2 years after the treatment was performed. Starting from 2020, all participating clinics report data on a regular, more frequent basis (33). Data availability lag time may therefore be reduced. Access to the register data for scientific research is applied from the regional health authority, after a dialogue with the authority. Applications are reviewed by a steering committee of the register.

The Swedish Medical Birth Register (SMBR) is managed by the National Board of Health and Welfare and has data since 1973. The register covers 100% of pregnancies when the child is born (live or stillbirth) after the gestational age of at least 22 weeks since July 2008 (week 28 before July 2008). Thus, no data on elective terminations or spontaneous abortions are available and information on stillbirths is only available from the gestational week 22 onwards (week 28 before July 2008). The register contains information reported by reproductive care, covering the duration of pregnancy and the infant period. The information recorded includes data on the mother (e.g. maternal diagnoses and exposures during pregnancy, including drug use since 1995), the delivery and the neonatal care. The data for the previous calendar year is usually available in December. Access to the register data for scientific research is applied from the National Board of Health and Welfare through a standard application procedure.

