9.9.3 Confounding by Baseline Characteristics

Confounding by baseline characteristics is a key challenge in non-interventional studies of drug treatment effects. Although the study drugs are equally recommended in IVF treatment guidelines and used interchangeably, differences in baseline characteristics, e.g., in terms of cause of infertility or previous IVF treatment, between the study cohorts cannot be ruled out. To minimize the potential for confounding, IPTW methods accounting for a broad range of characteristics, including history of IVF treatment, fertility-related health characteristics, and other factors potentially associated with the study outcomes will be applied.

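### Clinic enters the analysis only as private or public, so confounding by clinic practice remains wherever product use differs between clinics of the same type

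*Protocol*

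**What the plan says.** Section 9.7.3.1 estimates each pairwise PS by logistic regression, "including covariates as indicated in Table 1 (Section 9.3.2"). The only clinic-level entry in that table is "Type of clinic (private, public"), marked as a PS candidate. Two other care variables are PS candidates: treatment type and "GnRH protocol (agonist, antagonist").

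Four more care variables are listed for possible additional adjustment: trigger drug, luteal support drug, days of embryo cultivation and cryopreservation method. Section 9.3.2 says of variables determined after the gonadotropin is chosen: "These variables will therefore not be included in the PS but may instead be added as independent covariates in the IPTW-weighted regression model".

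On product choice, Section 9.9.3 begins: "Although the study drugs are equally recommended in IVF treatment guidelines and used interchangeably". Section 9.4.2 describes the Swedish IVF register as covering "all IVF clinics in Sweden (currently, 6 public and 13 private"), which is 19 clinics. Section 9.4 says that for Denmark "demographics (age, sex, geographical region), migration and vital statistics data" are registered electronically, and it places the same items for Sweden in the Total Population Register.

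**The concern.** By the protocol's own description in Section 9.7.3.1, inverse probability weighting removes confounding from the covariates in the PS model. A two-level clinic variable balances the private/public mix and nothing finer. Two cohorts balanced on every Table 1 variable can still have been treated in different laboratories under different policies.

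The protocol accepts that practice differs between clinics. Sections 9.2.2 and 9.9.2 report that Danish clinics followed different embryo-banking practices until about 2015. The limitations in Sections 9.9.3 and 9.9.4 cover patient characteristics and missing ovarian-reserve markers, and are silent on clinic practice.

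If product use differs between clinics of the same type, a difference in clinic performance would be reported as a product effect in LBR, CLBR and MC-CLBR. A larger sample does not reduce such a bias, and nothing planned would reveal it. The results are meant to show whether the reference product should be preferred in routine practice (Section 8), and the study also feeds a cost-effectiveness model (Section 14.3.4).

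**Working it through.** **1. Where clinic or region could enter**

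- Covariate list (Table 1): private/public only; no clinic, no region.
- PS model (Section 9.7.3.1): Table 1 candidates only.
- Outcome model (Section 9.7.3.4): weights, variables still unbalanced after weighting, optional post-initiation covariates. Estimating equations are mentioned, but no clinic level is named.
- Strata (Section 9.7.3.6): age and GnRH protocol.
- Sensitivity analyses (Table 8): exposure window, MC-CLBR approach, follow-up, oocyte yield, FET linkage, laboratory results.

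Neither treating clinic nor region appears in any of these. In Sweden, 19 clinics become 2 levels.

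**2. The scale of effect the study seeks**

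Section 9.5 uses a comparator MC-CLBR of 50%, requires the lower 95% limit of the odds ratio to exceed 1, and takes 75% of the anticipated women as eligible. At 50% this is close to 1.96 × SE, with SE = √(0.25/n1 + 0.25/n2). Solving the odds-ratio rule gives the same results to two decimals:

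| Comparison | Women at 75% (reference vs comparator) | Computed, points | Stated, points |
|---|---|---|---|
| Denmark, HP-hMG | 14,250 vs 9,000 | 1.32 | 1.5 |
| Sweden, HP-hMG | 13,500 vs 12,750 | 1.21 | 1.5 |
| Denmark, biosimilar | 10,500 vs 2,250 | 2.28 | 2.5 |
| Sweden, biosimilar | 8,250 vs 7,500 | 1.56 | 2.0 |

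Rounded up to the Table 3 grid, the computed values reproduce the stated ones. Individual Table 3 cohort sizes differ from the formula by up to about 8%, which does not affect this point.

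**3. Spurious difference with no true product effect**

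Within one clinic type:

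bias = (difference between products in the share of cycles at the better-performing clinics) × (success gap between the clinics)

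The inputs below are assumptions, because the protocol gives none. Take two equal-sized groups of clinics (100 cycles each) with LBR 25% and 30%.

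- Biosimilar shares 20% and 60%: reference (80×25 + 40×30)/120 = 26.67%; biosimilar (20×25 + 60×30)/80 = 28.75%; difference 2.08 points. By the formula: (60/80 − 40/120) × 5 = 0.417 × 5 = 2.08.
- Biosimilar shares 30% and 50%: reference (70×25 + 50×30)/120 = 27.08%; biosimilar (30×25 + 50×30)/80 = 28.13%; difference 1.04 points.

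Here the biosimilar looks better. With the shares reversed, the reference product would. Only the gap in success matters, not its level, so a 5-point gap in MC-CLBR gives the same result.

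**4. Range**

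With a share difference of 0.1 to 0.6 and a success gap of 2 to 10 points, the bias runs from 0.1 × 2 = 0.2 to 0.6 × 10 = 6.0 points. A share difference of 0.30 with a 5-point gap gives 1.5 points.

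**5. Effect on significance**

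With the standard errors from step 2 and no allowance for weighting, a pure bias of 1.5 points would be declared significant in 61% (Denmark, HP-hMG), 68% (Sweden, HP-hMG), 25% (Denmark, biosimilar) and 47% (Sweden, biosimilar) of studies, against a nominal 5%.

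**The case against.** - **Background care is not wholly uncontrolled.** A reader might infer from the single clinic variable that it is. Treatment type and GnRH protocol are PS candidates, results are stratified by GnRH protocol, and four further care variables may be adjusted for. This stands as a limit on the point. However, the four are optional and arise after drug choice, so adjusting for them may condition on consequences of treatment.
- **Clinic-level product choice is not documented.** A reader might infer that clinics or regions chose each product. No section says so. Interchangeable use (Section 9.9.3) and brand exchange at the pharmacy (Section 9.2.2) are equally compatible with mixing within clinics. The bias is plausible, not shown.
- **Section 9.1.1 is about time.** A reader might take "elective single embryo transfers rather than double embryo transfers" and the changes listed with it as evidence of differences between clinics. The text describes change over the study period. The embryo-banking passages are the protocol's only direct support for practice varying between clinics.
- **The size rests on assumed inputs.** This is correct: a range of 0.2 to 6.0 points neither establishes nor excludes a material bias.
- **Adjustment has a cost.** If product use follows clinic closely, putting clinic into the main PS strains positivity, and dropping single-product clinics departs from the overall-population effect that Section 9.7.3.1 sets as the target. This stands, and it argues for an analysis beside the main one, not in place of it.
- **Feasibility is uncertain.** No section says that a clinic identifier will be delivered, and Section 10.1 refers to protecting the privacy of providers. Swedish region sits in the Total Population Register, which is not among the study databases listed in Section 9.4.

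Deferring the matter to the SAP is a weak answer. Table 1 is the protocol's covariate list, and the variable has to be obtained through the data permits, a process that Section 6 runs from March to December 2021.

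**Conclusion.** The point holds in a limited form. Clinic is represented only by private/public, and no planned analysis uses treating clinic or region. Residual confounding by clinic practice is therefore unaddressed wherever product use differs between clinics of the same type.

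The size cannot be derived from the protocol. Under the assumed 5-point success gap it is 1.0 to 2.1 points, the same order as the stated detectable differences of 1.5 to 2.5 points. If products are well mixed within clinics, the bias is small. The plan as written gives no means of telling which case applies. It should be changed, but the protocol does not show that the main comparison is in fact biased.

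**What to change.** 1. Request a pseudonymised treating-clinic identifier in the Danish and Swedish data permits.
2. Report product share by clinic, and covariate balance by clinic after weighting.
3. Add to Table 8 a pre-specified sensitivity analysis of LBR, CLBR and MC-CLBR with clinic as a categorical variable in each pairwise PS, or with the PS estimated within clinic. Restrict it to clinic-periods that used both products, and report the number of cycles removed.
4. If the identifier is refused, use region by clinic type where region is obtainable. For Sweden this may need the Total Population Register as an additional source, and in both countries it is the woman's region of residence, not the clinic's location.
5. Name clinic practice as a possible source of residual confounding in Section 9.9.4.

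The cost is one further variable in the permits (possibly a further register for Sweden under the fallback), larger weights, loss of cycles from single-product clinics and wider intervals. The resulting estimate applies to clinics using both products, not to the overall population, which is why it should stand beside the main analysis and leave that analysis unchanged.
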